9. PRE-STUDY AND CONCOMITANT INTERVENTION/MEDICATION

Concomitant medications will be documented during screening and updated during the study. Disallowed medications for this study include: Any ocular medications with the exception of rewetting drops.

Concomitant therapies that are disallowed include: Any therapies that may contraindicate lens wear.

10. DEVIATIONS FROM THE PROTOCOL

Investigator will notify study sponsor upon identification of a protocol deviation. Major protocol deviations must be reported to the sponsor within 24 hours after discovery of the protocol deviation. The Investigator will report deviations per IRB/IEC requirements. All deviations will be tracked and corrective actions implemented as appropriate.

If it becomes necessary for the Investigator to implement a deviation in order to eliminate an immediate hazard to the trial subject, the Investigator may implement the deviation immediately without notification to the sponsor. Within 24 hours after the implemented deviation, the Investigator must notify and provide the rationale to the Sponsor and, as required, the IEC/IRB.

11. STUDY TERMINATION

If more than 2 subjects in the investigational soft contact lens group develop serious expected (eg, definite or probable MK) or unexpected device related adverse events, the study will be suspended. Upon review and consultation with IRB, DMC, and JJVC safety review committee, the study may be terminated.

The occurrence of one or more Unanticipated Serious Adverse Device Effect (USADE), or any SAE where the relationship to study agent cannot be ruled out, may result in stopping further dispensing of test article. In the event of a USADE or SAE, the Sponsor may unmask the treatment regimen for the subject(s) and will discuss this with the Investigator before any further subjects are enrolled.

The Sponsor will determine when a study will be stopped. The Principal Investigator always has the discretion to initiate stopping the study based on patient safety or if information indicates the study's results are compromised.

JJVC reserves the right to terminate the study at any time for any reason. Additionally, the IEC/IRB reserves the right to terminate the study if an unreasonable risk is determined. The study can be terminated by the Principal Investigator at the individual clinical site due to specific clinical observations, if in their opinion, after a discussion with JJVC, it is determined that it would be unwise to continue at the clinical site.

JJVC (and the IEC/IRB and DMC, if applicable) will evaluate all adverse events. If it is determined that an adverse event presents an unreasonable risk, the investigation, or that part of the investigation presenting the risk, will be terminated, as soon as possible.

Should the study be terminated (either prematurely or as scheduled), the Investigator will notify the IEC/IRB and Regulatory Authority as required by local regulatory requirements.

12. PROCEDURE FOR HANDLING PRODUCT QUALITY COMPLAINTS

A Product Quality Complaint (PQC) refers to any written, electronic, or oral communication that alleges deficiencies related to the identity, quality, durability, reliability, safety, effectiveness or performance of test articles after they have been released for clinical trial use.

Potential complaints may come from a variety of sources including but not limited to subjects, clinical research associates (CRA), clinical operations managers (COM), medical monitors, and site personnel, etc. The following are not considered product quality complaints:

- Subject satisfaction inquiries reported via “Subjective Questionnaires” and “Patient Reported Outcomes (PRO)”.
- Clinical test articles that are stored improperly or damaged after receipt at the investigational site.
- Lens replacements that occur due to drops/fall-outs.
- Damage deemed by clinicians or clinical staff to be caused by handling by the user, and not indicative of a quality deficiency (ie, tears, rips, etc), only in situations where there is no deficiency alleged by the subject.

Within 24 hours of site personnel becoming aware that a PQC has occurred, the PQC must be recorded in the EDC system, which will trigger an automatic email notification to the appropriate COM/CRA and Clinical QA representative. In cases where the EDC system in use is not configured to send automatic notifications or when an EDC system is not used, the COM/CRA is responsible for notifying Clinical QA upon discovery that a PQC has occurred.

Upon receipt of the EDC notification, the COM/CRA will contact the study site to collect additional information which will include:

- Date the complaint was received/recorded in the EDC System (Date of Sponsor Awareness)
- Who received the complaint
- Study number
- Clinical site information (contact name, site ID, telephone number)
- Lot number(s)
- Unique Subject Identifier(s)
- Indication of who first observed complaint (site personnel or subject)
- OD/OS indication, along with whether or not the lens was inserted
- Any related AE number if applicable

- Detailed complaint description (scheduled/unscheduled visit, wear time, symptoms, resolution of symptoms, etc)
- Eye Care Provider objective (slit lamp) findings if applicable
- Confirmation of product availability for return (and tracking information, if available), or rationale if product is not available for return ([REDACTED] for test article return instructions)

Once a complaint is received, it will be assessed by the COM, CRA, or trained site personnel to determine if it is an Adverse Event/Serious Adverse Event (AE/SAE). If the complaint results in an AE/SAE, the COM/CRA, or trained site personnel will follow Section 13 of this protocol. If the AE/SAE was potentially the result of a product quality related deficiency, these procedures also applies and will be executed in parallel.

In some cases, a PQC form may be generated in EDC by the site in error. In this event, the PQC forms will be marked “Intentionally Left Blank” or “ILB”. Justification for ILB must be documented.

13. ADVERSE EVENTS

13.1. Definitions and Classifications

Adverse Event (AE) – An AE is any untoward (unwanted) medical occurrence in a patient or clinical investigation subject administered a test article, study treatment or study procedure whether or not caused by the test article, study treatment or procedure. An AE can therefore be any unfavorable or unintended sign (including an abnormal finding), symptom, or disease temporally associated with the use of the test article, study treatment, or study procedure whether or not related to the test article, study treatment, or study procedure.

An AE includes any condition (including a pre-existing condition) that:

1. Was not present prior to the study , but appeared or reappeared following initiation of the study
2. Was present prior to the study, but worsened during the study. This would include any condition resulting from concomitant illnesses, reactions to concomitant medications, or progression of disease states
3. Pregnancy must be documented as an adverse event and must be reported to the clinical monitor and to the Sponsor immediately upon learning of the event

Serious Adverse Event (SAE) – An SAE is any untoward medical occurrence that:

- Results in death
- Is life threatening
- Requires in-patient hospitalization or prolongation of existing hospitalization
- Results in persistent or significant disability/incapacity (eg, a sight threatening event, a significant persistent or permanent change, impairment, damage, or disruption to the subject’s body)
- Is a congenital anomaly/birth defect, or

- Requires intervention to prevent permanent damage (the use of the test article resulting in a condition which requires medical or surgical intervention to preclude permanent impairment of the body structure or a body function). Important medical events that may not result in death, be life-threatening, or require hospitalization may be considered an SAE when, based upon appropriate medical judgment, they may jeopardize the patient or subject and may require medical or surgical intervention to prevent one of the outcomes listed in the above definition.

Diagnoses and conditions that are considered Ocular Serious Adverse Events include, but not limited to:

- Microbial Keratitis (MK)
- Iritis (including cells in the anterior chamber)
- Permanent decrease in best spectacle corrected visual acuity equivalent to 2 acuity lines or greater
- Central Corneal Opacity
- Central Corneal Neovascularization
- Uveitis
- Endophthalmitis
- Hypopyon
- Hyphemia
- Penetration of Bowman's Membrane
- Persistent Epithelial Defect
- Limbal cell Damage leading to Conjunctivalization

Significant Adverse Events – Those events that are usually symptomatic and warrant discontinuation (temporary or permanent) of the test article (excluding Serious Adverse Events).

Diagnoses and conditions that are considered Ocular Significant Adverse Events include, but not limited to the following:

- Contact Lens Induced Peripheral Ulcer (CLPU)
- Significant Infiltrative Events (SIE)
- Superior Epithelial Arcuate Lesions (SEALs)
- Any Temporary Loss of > 2 Lines of BSCVA
- Other Grade 3 or higher corneal findings, such as abrasions or edema
- Non-contact lens related corneal events - eg, Epidemic Keratoconjunctivitis (EKC)
- Asymptomatic Corneal Scar
- Any corneal event which necessitates temporary lens discontinuation > 2 weeks

Non-Significant Adverse Events – Those conditions that are usually asymptomatic and usually do not warrant discontinuation (temporary or permanent) of the test article. However, the Investigator may choose to treat as a precautionary measure.

Diagnoses and conditions that are considered Ocular Non-Significant Adverse Events include, but not limited to the following:

- Non-significant Infiltrative Event (NSIE)
- Contact Lens Papillary Conjunctivitis (CLPC)
- Superficial Punctate Keratitis (SPK)
- Conjunctivitis: Bacterial, Viral, Allergic
- Blepharitis
- Meibomianitis
- Contact Dermatitis
- Localized Allergic Reactions
- Any corneal event not explicitly defined as serious or significant adverse event, which necessitates temporary lens discontinuation < 2 weeks

Adverse Device Effect (ADE) – A sub-set of AEs, and include only those adverse events that are cause by or related to the investigational device.

Unanticipated Adverse Device Effect (UADE) – Any serious adverse effect on health or safety or any life-threatening problem or death caused by, or associated with, the test article, if that effect, problem, or death was not previously identified in nature, severity, or degree of incidence in the investigational plan, Investigator’s Brochure or protocol, or any other unanticipated serious problem associated with the test article that relates to the rights, safety and welfare of subjects.

13.2. Assessing Adverse Events

In conjunction with the medical monitor, the Investigator will evaluate adverse events to ensure the events are categorized correctly. Elements of categorization will include:

- Seriousness/Classifications (see definition in Section 13.1)
- Causality or Relatedness – ie, the relationship between the test article, study treatment or study procedures and the adverse event (not related; doubtful; possible; probable; very likely - see definition in Section 13.2.1)
- Adverse Event Severity – Adverse event severity is used to assess the degree of intensity of the adverse event (mild; moderate; severe for all events - see definition in Section 13.2.2).
- Outcome – Not Recovered or Not Resolved; Recovering or Resolving; Recovered or Resolved with Sequelae; Recovered or Resolved; Death Related to Adverse Event; Unknown
- Actions Taken – None; temporarily discontinued; permanently discontinued; other action taken

13.2.1 Causality Assessment

Causality Assessment – A determination of the relationship between an adverse event and the test article, study treatment, or study procedure. The test article, study treatment or study procedure relationship for each adverse event shall be determined by the Investigator using these explanations:

- Not Related- An adverse event that is not related to the use of the test article, study treatment or study procedures.

- **Doubtful** – An adverse event for which an alternative explanation is more likely, eg, concomitant treatment, concomitant disease(s), or the relationship of time suggests that a causal relationship is unlikely.
- **Possible** – An adverse event that might be due to the use of the test article, or to the study treatment or study procedures. An alternative explanation, eg, concomitant treatment, concomitant disease(s), is inconclusive. The relationship in time is reasonable. Therefore, the causal relationship cannot be excluded.
- **Probable** – An adverse event that might be due to the use of the test article. The relationship in time is suggestive (eg, confirmed by de-challenge). An alternative explanation is less likely, eg, concomitant treatment or concomitant disease(s).
- **Very Likely** – An adverse event that is listed as a possible adverse effect (device) or adverse reaction (drug) and cannot be reasonably explained by an alternative explanation, eg, concomitant treatment or concomitant disease(s). The relationship in time is very suggestive, eg, it is confirmed by de-challenge and re-challenge.

13.2.2 Severity Assessment

Severity Assessment – A qualitative assessment of the degree of intensity of an adverse event as determined by the Investigator or reported to him/her by the subject. The assessment of severity is made irrespective of test article, study treatment or study procedure relationship or seriousness of the event and should be evaluated according to the following scale:

- **Mild** – Event is noticeable to the subject, but is easily tolerated and does not interfere with the subject’s daily activities
- **Moderate** – Event is bothersome, possibly requiring additional therapy, and may interfere with the subject’s daily activities
- **Severe** – Event is intolerable, necessitates additional therapy or alteration of therapy and interferes with the subject’s daily activities

13.3. Documentation and Follow-Up of Adverse Events

The recording and documenting of adverse events (ocular and non-ocular) begins when the subjects are exposed to the test article, study treatment or study procedure. Adverse events reported before the use of test article, start of study treatment, or study procedures will be recorded as medical history. However, if the condition deteriorates at any time during the study it will be recorded and reported as an AE. Untoward medical events reported after the subject’s exit from the study will be recorded as adverse events at the discretion of the Investigator.

Upon finding an adverse event, the Principal Investigator will document the condition in the subject record and in the eCRFs. He/she will complete the Adverse Event /eCRF.

Complete descriptions of all adverse events must be available in the subject record. All Adverse Events including local and systemic reactions not meeting the criteria for “serious adverse events” shall be captured on the appropriate case report form or electronic data system. All adverse events occurring while the subject is enrolled in the study must be documented appropriately regardless of relationship.

It is the Investigator's responsibility to maintain documentation of each reported adverse event. All adverse events will be followed in accordance with applicable licensing requirements. Such documentation will include the following:

- Adverse event (diagnosis not symptom)
- Drawings or photographs (where appropriate) that detail the finding (eg, size, location, and depth, etc)
- Date the clinical site was notified
- Date and time of onset
- Date and time of resolution
- Adverse event classification, severity, and relationship to test articles, as applicable
- Treatment regimen instituted, including concomitant medications prescribed, in accordance with applicable licensing requirements
- Any referral to another health care provider if needed
- Outcome, ocular damage (if any)
- Likely etiology
- Best corrected visual acuity at the discovery of the event and upon conclusion of the event

In addition, if an infiltrate(s) is present, he/she will complete the Corneal Infiltrate Assessment /eCRF. Where necessary, a culture of the corneal lesion will be collected to determine if the infection is microbial in nature. If cultures are collected, the date of culture collection and laboratory utilized will be recorded.

Changes in the severity of an AE shall be documented to allow an assessment of the duration of the event at each level of intensity to be performed. Adverse events characterized as intermittent require documentation of the onset and duration of each episode. Changes in the assessment of relationship to the Test Article shall also be clearly documented.

Subjects who present with an adverse event shall be followed by the Investigator, within licensure, until all signs and symptoms have returned to pre-treatment status, stabilized, or been satisfactorily resolved. If further treatment beyond licensure is required, the patient will be referred to the appropriate health care provider. The Investigator will use his/her clinical judgment as to whether or not a subject reporting with an adverse event will continue in the study. If a subject is discontinued from the study, it will be the responsibility of the Investigator to record the reason for discontinuation. The Investigator will also document the adverse event appropriately and complete the Adverse Event /eCRF. Any subjects with ongoing adverse events related to the test article, study treatment or study procedures, as of the final study visit date should be followed to resolution of the adverse event or until referral to an appropriate health care provider, as recommended by the Investigator.

13.4. Reporting Adverse Events

The Investigator will notify the Sponsor of an adverse event by e-mail, facsimile, or telephone as soon as possible and no later than 24 hours from discovery for any serious /significant adverse events, and 2 days from discovery for any non-significant adverse event. In addition, a written report will be submitted by the Principal Investigator to the IEC/IRB

according to their requirements (Section 13.4.2). The report will comment whether or not the adverse event was considered to be related to the test article, study treatment or study procedures.

13.4.1 Reporting Adverse Events to Sponsor

Serious/Significant Adverse Events

The Investigator will inform the sponsor of all serious/significant adverse events occurring during the study period as soon as possible by e-mail, fax, or telephone, but no later than 24 hours following discovery of the event. The Investigator is obligated to pursue and obtain information requested by the Sponsor in addition to that information reported on the eCRF. All subjects experiencing a serious/significant adverse event must be followed up and all outcomes must be reported.

When medically necessary, the Investigator may break the randomization code to determine the identity of the treatment that the subject received. The Sponsor and study monitor should be notified prior to unmasking the test articles.

In the event of a serious/significant adverse event, the Investigator must:

- Notify the Sponsor immediately
- Obtain and maintain in the subject's records all pertinent medical information and medical judgment for colleagues who assisted in the treatment and follow-up of the subject
- Provide the Sponsor with a complete case history which includes a statement as to whether the event was or was not related to the use of the test article
- Notify the IEC/IRB as required by the IEC/IRB reporting procedure according to national regulations

Unanticipated (Serious) Adverse Device Effect (UADE)

In the event of an Unanticipated (Serious) Adverse Device Effect (UADE), the Investigator will submit a report of the UADE to the Sponsor and IEC/IRB as soon as possible, but no later than 24 hours after the Investigator first learns of the effect. This report is in addition to the immediate notification mentioned above.

The Sponsor must conduct an evaluation of the UADE and must report the results of the evaluation to FDA, the IEC/IRB and participating Investigators within 10 working days after the Sponsor first receives notification of the effect.

Non-Serious Adverse Events

All non-serious adverse events, including non-serious adverse device effects, will be reported to the sponsor by the Investigator no later than 2 days from discovery.

13.4.2 Reporting Adverse Events to the Responsible IEC/IRB and Health Authorities

Adverse events that meet the IEC/IRB requirements for reporting must be reported within the IEC/IRB's written guidelines. Each clinical site will refer to and follow any guidelines set

forth by their Approving IEC/IRB. Each clinical site will refer to and follow any guidelines set forth by their local governing Health Authorities.

The Sponsor will report applicable Adverse Events to the local health authorities according to the written guidelines, including reporting timelines.

13.5. Event of Special Interest

Not Applicable.

13.6. Reporting of Pregnancy

Subjects reporting pregnancy (by self-report) during the course of the study will be discontinued after the event is recorded as an Adverse Event. Once discontinued, pregnant participants and their fetuses will not be monitored for study related purposes. At the Investigator's discretion, the study participant may be followed by the Investigator through delivery. However, this data will not be collected as part of the clinical study database. Pregnant participants are not discontinued from contact lens or solution related studies for safety concerns, but due to general concerns relating to pregnancy and contact lens use. Specifically, pregnant women are discontinued due to fluctuations in refractive error and/or visual acuity that occur secondary to systemic hormonal changes, and not due to unforeseen health risks to the mother or fetus.

14. STATISTICAL METHODS

14.1. General Considerations

All data summaries and statistical analyses will be performed using the SAS software Version 9.4 (SAS Institute, Cary, NC). Throughout the analysis of data, the results for each subject/eye will be used when available for summarization and statistical analysis. Unscheduled visits will be summarized separately and will be excluded from the statistical analysis.

Summary tables (Descriptive statistics and/or frequency tables) will be provided for all baseline variables, efficacy variables and safety variables as appropriate. Continuous variables will be summarized with descriptive statistics (n, mean, standard deviation [SD], median, minimum and maximum). Frequency count and percentage of subjects or eyes within each category will be provided for categorical data.

Summaries will be presented by study lens type and will be performed separately by completion status. All analyses will be conducted on per-protocol population (see Section 14.3).

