8. SUBJECTS COMPLETION/WITHDRAWAL

8.1. Completion Criteria

Subjects are considered to have completed the study if they:

- provided informed consent;
- they are eligible;
- have not withdrawn/discontinued for any reason described in Section 8.2;
- Complete all study visits

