8.2. Withdrawal/Discontinuation from the Study

A subject will be withdrawn from the study for any of the following reasons:

- Subject death during the study period
- Subject withdrawal of consent
- Subject not compliant to protocol
- Subject lost to follow-up
- Subject no longer meets eligibility criteria (eg, the subject becomes pregnant)
- Subject develops significant or serious adverse events causing discontinuation of study lens wear
- Subjects who have experienced a Corneal infiltrative Event (CIE)
- Investigator's clinical judgment regarding the subject safety reasons (that it is in the best interest of the subject to stop treatment)
- Subject not compliant with study lens wear schedule
- Subject not successfully dispensed due to lack of efficacy and safety including poor vision, poor comfort or unacceptable fit

For discontinued subjects, the Investigator will:

- Complete the current visit (scheduled or unscheduled)
- Complete the Final Evaluation, indicating the reason that the subject was discontinued from the study
- Record the spherocylindrical refraction with best corrected distance visual acuity
- Collect used test article(s) (worn or brought to the visit) from the subject and discard them, unless otherwise stated in Section 7.2
- Collect all unused test article(s) from the subject

An additional subject may be enrolled if a subject discontinues from the study prematurely.

In cases where a subject is lost to follow-up, every possible effort must be made to contact the subject and determine the reason for discontinuation/withdrawal. The measures taken to follow up must be documented including two written attempts and a certified letter (or equivalent) as the final attempt.

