14.3. Analysis Populations

Safety Population:

All subjects who were administered any test article excluding subjects who drop out prior to administering any test article. At least one observation should be recorded.

Per-Protocol Population:

All subjects who have successfully completed all visits and did not substantially deviate from the protocol as determined by the trial cohort review committee prior to database hard lock (Per-Protocol Population). Justification of excluding subjects with protocol deviations in the per-protocol population set will be documented in a memo to file.

Intent-to-Treat (ITT) Population:

All randomized subjects regardless of actual treatment and subsequent withdrawal from study or deviation from protocol. At least one observation should be recorded.

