14.5. Primary Analysis

Primary efficacy analysis:

The CLUE handling score will be analyzed using a linear mixed model. The model will include the experimental design factors: sequence of lens wear, lens wearing period and lens type as fixed effects. Site and subject nested in site will be included as random effects. Age and gender will be included as fixed covariates when appropriate. The covariance between residual errors from the same subject across lens wearing periods will be selected based on the finite-sample corrected Akaike's Information Criterion (Keselman et al. 1998²). Covariance structures considered may include: Homogenous compound symmetry (CS) and Unstructured covariance structure (UN). The structure that returns the lowest Akaike Information Criteria Corrected (AICC) will be selected as the structure that best fit the data.

Comparisons between each Test lens and Control lens will be carried out using 95% confidence intervals constructed of least-square means (LSM) differences (Test minus Control) from the linear mixed models. Non-inferiority will be concluded if the lower confidence limit is greater than -5 points.

In all models, the Kenward and Roger method (Kenward and Roger, 1997) will be used for the calculation of the denominator of degrees of freedom.

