14.9. Procedure for Handling Missing Data and Drop-Outs

Missing or spurious values will not be imputed. The count of missing values will be included in the summary tables and listings.

Subject dropout is expected to be one of the main reasons of missing data in this clinical trial. Past clinical trials don't provide the evidence that subject dropout is systematic or not-at-random. To evaluate the impact of missing data, sensitivity analysis will be conducted using multiple imputation methods if the proportion of subject dropout is greater than the 15%. The SAS/STAT procedures PROC MI and PROC MIANALYZE will be utilized with a parametric regression method used to make at least 5 imputations.

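### All model contrasts rest on completers; ITT is defined but never used, and the imputation in 14.9 has no stated population

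*Combined protocol and SAP*

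**What the plan says.** Section 14.1 sets one population for everything: "All analyses will be conducted on per-protocol population (see Section 14.3"). Section 14.3 defines that population as "All subjects who have successfully completed all visits and did not substantially deviate from the protocol". Under 8.1 a subject counts as completed only if they "have not withdrawn/discontinued for any reason described in Section 8.2", and one of the 8.2 reasons is "Subject not successfully dispensed due to lack of efficacy and safety including poor vision, poor comfort or unacceptable fit".

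Section 14.3 also defines an ITT set, "All randomized subjects regardless of actual treatment and subsequent withdrawal from study or deviation from protocol", with at least one recorded observation. No later section assigns an analysis to it: 14.5 names no population and 14.6 repeats the 14.5 method. The decision rule in 14.5 is "Non-inferiority will be concluded if the lower confidence limit is greater than -5 points".

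Two provisions reach beyond completers. Section 14.1 adds that "Summaries will be presented by study lens type and will be performed separately by completion status". Section 14.9 imputes nothing in the main analysis but says "sensitivity analysis will be conducted using multiple imputation methods if the proportion of subject dropout is greater than the 15" per cent, without naming the population or the contrast.

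**The concern.** The trial is a five-period crossover, so a subject who leaves at lens 2 or later may already have given handling scores. The 14.5 mixed model can use such partial sequences, but the per-protocol restriction removes them from every contrast. This includes a subject who attends both visits and fails fit at the fifth lens, because 8.1 and 8.2 together make that subject a non-completer.

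The toric fit and lens fit steps (1.21 and 1.22 and their repeats) end participation because of the lens then being worn, so exit need not be unrelated to lens type. Section 14.9 relies on past trials giving no evidence of systematic dropout and does not address exits of this kind.

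As planned, the report would contain no contrast showing whether the -5 conclusion also holds in all randomised subjects. Some precision would also be given up, although the target of 80 completers is already below the smallest sample size in the 14.2 table (87).

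**Working it through.** **1. Which subjects each analysis covers**

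| Item | Population in the text | Contrast against -5? |
|---|---|---|
| 14.5 primary, 14.6 secondary | Per-protocol, through 14.1 | Yes |
| 14.1 summaries by completion status | Completers and non-completers | No, descriptive only |
| 14.9 multiple imputation | Not named; per-protocol if 14.1 governs | Not stated |
| ITT (14.3) | All randomised with an observation | No analysis assigned |

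If 14.1 governs 14.9, the imputation runs on a set from which dropouts have been removed, so there is no dropout to impute. It serves its stated purpose only in a wider set, which the text does not name.

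**2. When the 15% trigger is reached**

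With k randomised leavers beside 80 completers, dropout is k/(80 + k). For k = 14 this is 14/94 = 14.9%; for k = 15 it is 15/95 = 15.8%. So at least 15 must be lost after randomisation, if exactly 80 complete. The 100 and 80 are approximate targets. The synopsis counts eligible subjects as enrolled, step 1.1 only requires consent first, and 5.2 and 8.2 allow replacement. The dropout rate therefore cannot be fixed from the documents.

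**3. SD for the precision check**

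Section 14.2 does not print its SD. I used a paired non-inferiority t-test with margin 5 and SD of the difference = SD × √(2(1 − ρ)):

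- The plan's figures are 116, 87, 180 and 135.
- The CLUE population SD of 20 (section 2.2) gives 103, 78, 159, 120 at one-sided 2.5% and 81, 61, 126, 95 at one-sided 5%. Neither matches.
- SD 24.0 at one-sided 5% returns 116, 87, 180, 135.
- SD 21.25 at one-sided 2.5% returns 116, 88, 180, 135.

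I therefore carry 21.26 (the back-solved value for most rows at one-sided 2.5%) and 24.0 as assumed values, with the plan's correlations of 0.6 and 0.7.

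**4. Precision recovered by including leavers' scores**

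The design is the 10-sequence, 5-period Williams design with sequence, period and lens fixed. V = (1 − ρ)I + ρJ (compound symmetry), and the information is the sum of X′V⁻¹X over subjects. For 80 completers the contrast variance is SD² × 2(1 − ρ)/80. I then added k leavers, assuming their exits spread evenly over the five lenses.

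| k | Exit lens | Variance ratio, ρ = 0.6 / 0.7 | Effective completers = 80/ratio |
|---|---|---|---|
| 5 | unscored | 0.980 / 0.980 | 81.6 / 81.6 |
| 5 | scored | 0.968 / 0.969 | 82.6 / 82.6 |
| 10 | unscored | 0.961 / 0.962 | 83.3 / 83.2 |
| 10 | scored | 0.938 / 0.939 | 85.3 / 85.2 |
| 20 | unscored | 0.925 / 0.926 | 86.5 / 86.4 |
| 20 | scored | 0.884 / 0.885 | 90.5 / 90.4 |

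**5. Effect on the lower limit, k = 20**

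Shift = 1.96 × SE for 80 completers × (1 − √ratio).

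| SD | ρ | SE, 80 completers | Shift, unscored | Shift, scored |
|---|---|---|---|---|
| 21.26 | 0.6 | 21.26 × √0.0100 = 2.126 | 0.16 | 0.25 |
| 21.26 | 0.7 | 21.26 × √0.0075 = 1.841 | 0.14 | 0.21 |
| 24.0 | 0.6 | 24.0 × √0.0100 = 2.400 | 0.18 | 0.28 |
| 24.0 | 0.7 | 24.0 × √0.0075 = 2.078 | 0.15 | 0.24 |

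The shift is zero if all losses come before randomisation or before any score.

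**6. Is the exit lens scored?**

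An unacceptable toric fit (1.21) or lens fit (1.22) sends the subject to the Final Evaluation, ahead of the Post-Fit Questionnaire (1.23) and the Removal Questions (1.25). Steps F.1 and F.2 collect refraction, acuity and disposition only. Section 8.2, however, has the investigator finish the visit in progress for a discontinued subject. The two can be read differently, and the answer decides which rows of the tables apply.

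**The case against.** The case for leaving the plan alone has weight. Per-protocol is a sound primary set for non-inferiority, and the protocol calls this an initial evaluation with about 15 minutes of wear per lens. Section 14.9 is meant to assess the effect of dropout, so its sensible reading is a wider set, with ITT ready to hand. The summaries by completion status can show what leavers recorded. The precision at stake is a fraction of a CLUE point. All of this stands, and it limits the severity. It does not supply a stated all-randomised contrast, and below the 15% trigger no sensitivity analysis is planned at all.

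A reader might infer several stronger things that the documents do not support:

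- **That completers-only analysis tilts the result towards non-inferiority.** This needs exit to be related to handling of the lens in use and exits to fall unevenly across lenses. The fit criteria are examiner judgements of rotation, stability, centration, edge lift and movement, and nothing links them to handling scores. The cited study in 1.5 compared centre thickness, whereas this trial varies peripheral thickness. The same exit rule acting alike on all five lenses would largely cancel in the contrasts, and an opposite link would reverse the sign.
- **That leavers' scores are lost altogether.** They are lost to the contrasts but may appear in the descriptive summaries.
- **That dropout will be 20% and the trigger certain.** Some of the 20 may be lost before randomisation, and leavers may be replaced.
- **That an all-randomised model would remove any bias.** It cannot correct for an exit lens that was never scored.

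**Conclusion.** The point holds as a gap in the analysis plan. Every model contrast is confined to completers, ITT has no role, and the one planned missing-data check has no stated population and, on the literal text, nothing to impute.

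The demonstrable cost is modest: a 7-8% or 11-12% reduction in contrast variance forgone, or about 0.14 to 0.28 points on the lower limit. This rests on 20 randomised leavers, exits spread evenly over the lenses, compound symmetry, correlation 0.6 to 0.7 and a back-solved SD of 21.26 or 24.0. Fewer or earlier exits shrink it, to zero at the limit. Bias remains an open possibility of unknown size and direction.

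It is a cheap improvement of low to moderate severity, and no reason to replace the primary population.

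**What to change.** 1. Keep per-protocol as the primary population.
2. In 14.1 and 14.5, pre-specify a supporting analysis: the 14.5 model on all randomised subjects with at least one CLUE handling score, using all available periods and read against the same -5 limit. This gives the ITT set in 14.3 a use.
3. In 14.9, state that the imputation applies to that set and that the 15% is counted among randomised subjects.
4. Reconcile steps 1.21 and 1.22 and their repeats with 8.2 on whether the handling questions are completed for the lens in use at exit. The sponsor should settle which reading applies; no discontinuation rule needs to change for this point.
5. Optionally, add a not-at-random scenario for fit-related exits. This is a preference.

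The cost is SAP wording and one more run of a model already specified, with no added visits or subjects. The downside is that the conclusion may look slightly less favourable in the wider set.
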